## 6 Statistical considerations

### 6.1 Accrual and sample size calculations

Recruitment will target accruing a total of 24 healthy, HIV-1–uninfected adult participants in two treatment groups, with 12 participants assigned to each group.

In Group 1, all study participants will receive three IV administrations of VRC07-523LS at the 10 mg/kg dose level. In Group 2, all study participants will receive three IV administrations of VRC07-523LS at the 30 mg/kg dose level.

In both groups, the three infusions will be administered every 16 weeks.

Participants will be randomly assigned to either one of the groups. Groups 1 and 2 will open to randomization at the same time.

In Groups 1 and 2, every study participant will be followed for 12 months (including 8 months of product administration plus 4 months of follow-up) from the day of first product administration.

To ensure balance in the trial of both sexes assigned at birth, the trial will enroll at least and approximately 50% of participants assigned female sex at birth. Randomization will be stratified by assigned sex at birth to ensure balance within each treatment group.

The times at which samples will be collected are listed in [Table 9-1](#) and [Table 9-2](#) for each mucosal site and the blood.

Since enrollment is concurrent with the first biopsy sample collection, all participants will provide some data regarding tolerability of mucosal sample collections. For analyses of VRC07-523LS levels in serum and mucosa and of data from ADA assays, it is possible that data may be missing for various reasons, such as participants terminating from the study early, problems in shipping specimens, or high assay background. Immunogenicity data from 17 phase 1 and 2 phase 2a HVTN vaccine trials, which began enrolling after June 2005 (data as of September 2014), indicate that 17% is a reasonable estimate for the rate of missing data. In HVTN 104 (phase 1 trial of VRC01), approximately 10-15% of drug concentration data were missing at the primary timepoints.

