## 9.6 Mucosal sampling

Mucosal secretion and biopsy samples will be collected at the timepoints indicated in [Appendix D](#). All participants in this trial will have consented to mucosal specimen collections. Participants assigned male sex at birth will provide semen, rectal secretions, and rectal biopsies. Participants assigned female sex at birth will provide cervicovaginal and rectal secretions, as well as cervical, vaginal and rectal biopsies. Small (~2-4 mm) tissue biopsies are obtained from the vagina and ectocervix using a speculum and from the rectum by anoscopy by experienced clinicians. The product administration and biopsy collection schedules per mucosal compartment and visit are described in detail in [Table 9-1](#), and also outlined in [Appendix D](#); however, fewer samples may be taken based on the judgment of the performing clinician. The number of biopsies collected per mucosal compartment and visit is shown in [Table 9-2](#). Following the first product administration, a participant may decline all or some of the mucosal biopsies or secretion collections, but they should be encouraged to continue with any collections that they deem acceptable until the end of the trial.

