5 RANDOMIZATION

Participants will enroll in the study at the first biopsy collection. Only participants who remain in the trial after the completion of the first biopsy visit will be randomized.

Accrual will continue until 24 participants have received first product administration.

The randomization sequence will be obtained by computer-generated random numbers and provided to each HVTN CRS through the SDMC via a Web-based randomization system.

Groups 1 and 2 will be randomized simultaneously.

The randomization will be stratified by assigned sex at birth and done in blocks to ensure balance across both groups.

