Comparisons of dose-amount-adjusted, IgG-normalized VRC07-523LS concentrations between visits (v2 vs. v5, v2 vs. v7, v2 vs. v9, v4 vs. v6, v4 vs. v8, v6 vs. v8) are made using the Wilcoxon Signed-Rank test, and comparisons between sexes at birth at visits 4 and 5 are made using the Wilcoxon Rank Sum test. Additionally, comparisons of body-weight-adjusted, IgG-normalized VRC07-523LS concentrations between treatment arms at visits 4 and 5 are made using the Wilcoxon Rank Sum test. Comparisons are made for the % penetration of protein-normalized VRC07-523LS between visits, and specimen types using Wilcoxon Signed-Rank test; and between treatment arms using Wilcoxon Rank Sum test; and between sex at birth, controlling for treatment arms using Van Elteren Test. Comparisons are conducted between levels normalized using actual total protein concentrations and those normalized using the U.S. reference protein concentration (70 g/L) with treatment arms (T1 and T2) pooled using the Wilcoxon Signed Rank Test. Linear mixed-effect regression analyses are performed modeling natural log-transformed concentrations as a function of time since most recent infusion, sex at birth, and treatment group. Linear regressions are performed modeling the difference between natural log-transformed concentrations between visits adjusting for the difference between number of days since last infusion at compared visits, as well as sex at birth and treatment group. P-values are adjusted for multiple comparisons by controlling the false discovery rate (FDR) using the Benjamini-Hochberg procedure [9]

and the q-value [10]. Results are significant if the adjusted p-value or q-value ≤ 0.05 . Comparisons are conducted for groups with at least 3 data points for paired test and at least 5 for unpaired test.

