- For mucosal tissues, comparisons between visits 2 vs 9 dose normalized IgG-normalized VRC07-523LS concentrations (trough after a different number of infusions) using Wilcoxon signed-rank test, by specimen type. P-values will be adjusted for multiple comparisons by controlling the false discovery rate (FDR) using the Benjamini-Hochberg (BH) procedure and the q-value. The unadjusted p-values, BH-adjusted p-values, and q-values will be reported.
- For secretions, body-weight-adjusted IgG-normalized VRC07-523LS concentrations comparisons between treatment groups at visits 4 and 5 using Wilcoxon signed-rank test, by specimen type with sex at birth combined. P-values will be adjusted for multiple comparisons by controlling the false discovery rate (FDR) using the Benjamini-Hochberg (BH) procedure and the q-value. The unadjusted p-values, BH-adjusted p-values, and q-values will be reported.
- For mucosal tissues, body-weight-adjusted IgG-normalized VRC07-523LS concentrations comparisons between treatment groups at visit 4 using Wilcoxon signed-rank test, by specimen type with sex at birth combined. P-values will be adjusted for multiple comparisons by controlling the false discovery rate (FDR) using the Benjamini-Hochberg (BH) procedure and the q-value. The unadjusted p-values, BH-adjusted p-values, and q-values will be reported.
- Comparisons for body-weight-adjusted IgG-normalized VRC07-523LS concentration at peak timepoints (T1 vs T2) using Wilcoxon rank sum test, by specimen type and for (1) both assigned sexes at birth combined for rectal biopsies and rectal secretions and (2) each assigned sex at birth separately for other specimen types. P-values will be adjusted for multiple comparisons by controlling the false discovery rate (FDR) using the Benjamini-Hochberg (BH) procedure and the q-value. The unadjusted p-values, BH-adjusted p-values, and q-values will be reported.
- For rectal secretions, dose-amount-adjusted IgG-normalized VRC07-523LS concentrations comparisons at visit 4 and 5 among different sexes, using Wilcoxon rank sum test, by specimen type. P-values will be adjusted for multiple comparisons by controlling the false discovery rate (FDR) using the Benjamini-Hochberg (BH) procedure and the q-value. The unadjusted p-values, BH-adjusted p-values, and q-values will be reported.

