- For mucosal tissues, comparisons between visits 4 vs 8 penetration percentages (protein-normalized VRC07-523LS of mucosal divided by serum at Cmax after a different number of infusions) using Wilcoxon signed-rank test, by treatment group and spec type. P-values will be adjusted for multiple comparisons by controlling the false discovery rate (FDR) using the Benjamini-Hochberg (BH) procedure and the q-value. The unadjusted p-values, BH-adjusted p-values, and q-values will be reported.
- For mucosal tissues, comparisons between visits 2 vs 9 penetration percentages (protein-normalized VRC07-523LS of mucosal divided by serum at trough after a different number of infusions) using Wilcoxon signed-rank test, by treatment group and spec type. P-values will be adjusted for multiple comparisons by controlling the false discovery rate (FDR) using the Benjamini-Hochberg (BH) procedure and the q-value. The unadjusted p-values, BH-adjusted p-values, and q-values will be reported.
- For secretions, comparison of penetration percentages (protein-normalized VRC07-523LS of mucosal divided by serum) between treatment groups, using Wilcoxon rank sum test, at visits 4 and 5. P-values will be adjusted for multiple comparisons by controlling the false discovery rate (FDR) using the Benjamini-Hochberg (BH) procedure and the q-value. The unadjusted p-values, BH-adjusted p-values, and q-values will be reported.
- For mucosal tissues, comparison of penetration percentages (protein-normalized VRC07-523LS of mucosal divided by serum) between treatment groups, using Wilcoxon rank sum test, at visit 4. P-values will be adjusted for multiple comparisons by controlling the false discovery rate (FDR) using the Benjamini-Hochberg (BH) procedure and the q-value. The unadjusted p-values, BH-adjusted p-values, and q-values will be reported.
- For rectal secretions, comparison of penetration percentages (protein-normalized VRC07-523LS of mucosal divided by serum) at visits 4 and 5, among different sexes, controlling for treatment arms, using Van Elteren Test. P-values will be adjusted for multiple comparisons by controlling the false discovery rate (FDR) using the Benjamini-Hochberg (BH) procedure and the q-value. The unadjusted p-values, BH-adjusted p-values, and q-values will be reported.

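### The 10 vs 30 mg/kg tests in rectal specimens ignore sex, the randomisation stratum; the gap with no other remedy is rectal % penetration

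*SAP*

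**What the plan says.** On allocation, SAP section 5 and Protocol 6.2 agree: "The randomization will be stratified by assigned sex at birth and done in blocks to ensure balance across both groups". No other stratum is named. Protocol 6.1 plans two groups "with 12 participants assigned to each group", and says that "the trial will enroll at least and approximately 50% of participants assigned female sex at birth".

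On specimens, Protocol 9.6 states: "Participants assigned male sex at birth will provide semen, rectal secretions, and rectal biopsies". Women give cervicovaginal and rectal secretions and cervical, vaginal and rectal biopsies. Rectal secretions and rectal biopsies are therefore the only mucosal specimens from both sexes.

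On the arm comparisons, SAP 8.3.1 lists:

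- Body-weight-adjusted, IgG-normalised levels: secretions at visits 4 and 5 and tissues at visit 4, each "by specimen type with sex at birth combined". Both bullets name the Wilcoxon signed-rank test. A further bullet, on peak timepoints, uses the rank-sum test and combines the sexes for rectal specimens.
- % penetration in secretions: "between treatment groups, using Wilcoxon rank sum test, at visits 4 and 5". The tissue bullet is the same at visit 4. Neither mentions sex.

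The methods text in SAP 8.3 names the rank-sum test for the level comparison between arms. It compares penetration between the sexes "controlling for treatment arms using Van Elteren Test". It also lists mixed and linear models for log levels that contain both sex at birth and treatment group.

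**The concern.** When allocation is balanced within a stratum, the between-stratum difference largely cancels from the arm contrast. An analysis that leaves the stratum out still counts that difference as noise. If rectal levels or penetration differ by sex, the pooled rank-sum test runs below its nominal level and loses power.

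Comparing the dose regimens is secondary objective 1, in a trial of 24 people, and these tests are also adjusted for the false discovery rate. The SAP already applies a stratified rank test in the mirror-image comparison (sex, controlling for arm), so the omission for arm, controlling for sex, looks like an oversight.

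A wording conflict sits in the same place. The signed-rank test needs pairs, and participants in different arms are not paired, so the two level bullets as written cannot be carried out.

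**Working it through.** **Plan's own figure.** The documents give no power or type I error for any arm comparison. The nearest figures are the correlation powers in Protocol Table 6-3, and these reproduce. For n = 12 and r = 0.7, the transformed value is arctanh(0.7) + 0.7/22 = 0.899. The critical r is 0.576, with arctanh 0.656. Power is Φ((0.899 − 0.656) × √9) = 76.7%, as stated. For n = 24 and r = 0.5 the same method gives 72.6%, also as stated.

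**Inputs.** 12 per arm, two-sided 5% before FDR adjustment, and 6 women and 6 men per arm from the planned half-and-half split. Assumed, because the documents give neither: a sex difference of 0 to 2 within-sex SD, an arm effect of 1 SD, and normal errors on the log scale.

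**Tests.** Pooled rank-sum: W is the rank total of one arm among 24, with mean 12 × 25/2 = 150 and variance 12 × 12 × 25/12 = 300. Van Elteren: rank within each sex (N = 12), sum (R − 39)/13 over the two sexes, with variance 2 × (6 × 6 × 13/12)/13² = 0.46.

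**Results** (simulation, normal approximation):

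| Sex difference | Power, pooled | Power, stratified | Type I, pooled | Type I, stratified |
|---|---|---|---|---|
| 0 | 64% | 59% | 5.2% | about 4.5% |
| 0.5 SD | 61% | 59.5% | 4–5% | 4–5% |
| 1 SD | 53% | 59% | 3.0% | 4.5% |
| 1.5 SD | 41% | 59% | 1.4% | 4.5% |
| 2 SD | 28% | 59% | 0.5% | 4.7% |

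**Hand check of the type I error.** A half-and-half mixture of two groups d SD apart has variance 1 + d²/4, but with sex balanced across arms the arm contrast varies as if the variance were 1. The effective critical value is 1.96 × √(1 + d²/4). At d = 1 this is 2.19, giving 2.8%; at d = 2 it is 2.77, giving 0.6%. Both agree with the table.

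**Exact tests.** With exact versions, power is 60.8% vs 59.3% with no sex difference, 57.9% vs 59.0% at 0.5 SD, 49.7% vs 58.7% at 1 SD and 24.6% vs 59.1% at 2 SD. So part of the 64% vs 59% gap in the first row comes from the tests' differing type I error. With exact tests the cost of stratifying is 60.8 − 59.3 = 1.5 points.

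**Missing data.** Using the 17% in Protocol 6.1 and an arm effect of 1.2 SD, power is 68% vs 64% with no sex difference, 58% vs 65% at 1 SD and 34% vs 65% at 2 SD.

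**Levels with a 3-fold dose effect.** Body-weight-adjusted levels are not divided by dose, so a 3-fold ratio may carry through: log 3 = 1.10, or 1.10/SD in standardised units. Pooled versus stratified power (exact tests):

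| Log SD (assumed) | Sex difference 1 SD | Sex difference 2 SD |
|---|---|---|
| 0.6 | 97% vs 98% | 87% vs 98% |
| 0.8 | 79% vs 85% | 55% vs 86% |
| 1.0 | 59% vs 67% | 31% vs 67% |

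Penetration is a mucosa-to-serum ratio, so a 3-fold dose effect need not carry over to it.

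**The case against.** The strongest reply is that the dose comparison does not in fact ignore sex. The mixed model in SAP 8.3, listed in 8.3.1 for body-weight-adjusted IgG-normalised levels, contains sex at birth and treatment group. That is the same variable as in the pooled level tests, and secondary endpoint 1 is levels, not penetration. Protocol 6.4.4.1 also promises similar analyses stratified by sex. This stands for levels. It does not cover penetration: no table listed in 8.3.1 gives a sex-adjusted arm comparison of it.

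The second reply is that nothing in the documents shows a sex difference. A reader might infer that the SAP expects one because it tests for one, but planning a test is not a forecast. At or below about 0.5 SD the pooled test is as good, or slightly better. This also stands, and it limits the weight of the point.

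Third, pooling is explicit only for levels. For penetration it is inferred from the absence of any stratum. That is the natural reading, since the neighbouring sex comparison does name its stratum, but it remains an inference.

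A reader might also extend the point to serum. Serum comes from both sexes, but SAP 8.1.1 lists its between-group comparison without naming a test, so no serum defect is shown.

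**Conclusion.** The point holds for arm comparisons in rectal secretions and rectal biopsies. For IgG-normalised levels it is largely covered by the mixed model, and the loss is small if the 3-fold dose effect is large relative to the SD. For rectal % penetration nothing in the plan covers it.

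The size is conditional on an assumed sex difference: no gain from stratifying at or below about 0.5 SD, about 6 points of power at 1 SD (53% vs 59%), and about 31 points at 2 SD (28% vs 59%). These figures rest on 6 + 6 per arm, a 1 SD arm effect and normal errors.

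Two stronger readings are not supported. The plan does not risk excess false positives for this reason: the error is towards conservatism, so what could be missed is a real dose difference. Nor are the semen, cervicovaginal, cervical and vaginal comparisons affected, because each comes from one sex only.

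The signed-rank wording is a separate and certain inconsistency: SAP 8.3.1 and the methods text of SAP 8.3 name different tests for the same comparison of independent arms.

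**What to change.** 1. In SAP 8.3 and 8.3.1, use the Van Elteren test stratified by sex at birth for arm comparisons in rectal secretions and rectal biopsies, for both levels and % penetration. This includes the rectal part of the peak-timepoint bullet. Keep the plain rank-sum test for single-sex specimens.
2. In the two 8.3.1 bullets that compare treatment groups with a signed-rank test, and only those, write rank-sum (stratified by sex for rectal specimens), in line with SAP 8.3. Leave the paired visit comparisons alone, including visit 2 vs 9, where signed-rank is correct.
3. State that the SAP's minimum of 5 data points for unpaired tests applies to each arm's total. With 17% missing, a sex-by-arm cell of 6 is expected to hold 6 × 0.83 = 5.0 values, so applying the minimum within cells would often drop the test.

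The cost is SAP wording, plus a few points of power at most if the sexes do not differ: 64% vs 59% by normal approximation, or 1.5 points with exact tests.

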- For rectal biopsies, dose-amount-adjusted IgG-normalized VRC07-523LS concentrations comparisons at visit 4 among different sexes, using Wilcoxon rank sum test, by specimen type. P-values will be adjusted for multiple comparisons by controlling the false discovery rate (FDR) using the Benjamini-Hochberg (BH) procedure and the q-value. The unadjusted p-values, BH-adjusted p-values, and q-values will be reported.
- Specimen comparison using partial Spearman's rank correlation, adjusted for treatment arms (T1 and T2) and sex assigned at birth, stratified by visit. P-values will be adjusted for multiple comparisons by controlling the false discovery rate (FDR) using the Benjamini-Hochberg (BH) procedure and the q-value. The unadjusted p-values, BH-adjusted p-values, and q-values will be reported.
- Summary of the percentage of penetration for protein-normalized VRC07-523LS concentration, by specimen type, treatment arm, assigned sex at birth and visit.
- For secretions, comparisons between visits 4, 6, and 8 penetration percentages (protein-normalized VRC07-523LS of mucosal divided by serum at Cmax after a different number of infusions) using Wilcoxon signed-rank test, by specimen types with treatment groups combined. P-values will be adjusted for multiple comparisons by controlling the false

discovery rate (FDR) using the Benjamini-Hochberg (BH) procedure and the q-value. The unadjusted p-values, BH-adjusted p-values, and q-values will be reported.

- For secretions, comparisons between visits 2, 5, 7, and 9 penetration percentages (protein-normalized VRC07-523LS of mucosal divided by serum at trough after a different number of infusions after a different number of infusions) using Wilcoxon signed-rank test, by specimen types with treatment groups combined. P-values will be adjusted for multiple comparisons by controlling the false discovery rate (FDR) using the Benjamini-Hochberg (BH) procedure and the q-value. The unadjusted p-values, BH-adjusted p-values, and q-values will be reported.

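### Tissue penetration is compared between visits separately by arm, which leaves cervical and vaginal tissue about 6 women per test, while the matching secretion tests combine the arms

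*SAP*

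**What the plan says.** SAP 8.3.1 (List of Tables) plans two between-visit comparisons of tissue penetration, visit 4 versus 8 and visit 2 versus 9. Both are run "using Wilcoxon signed-rank test, by treatment group and spec type". The corresponding secretion tables are run "using Wilcoxon signed-rank test, by specimen types with treatment groups combined".

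The methods text in SAP 8.3 names the test without a split by arm: "Comparisons are made for the % penetration of protein-normalized VRC07-523LS between visits, and specimen types using Wilcoxon Signed-Rank test". Two related sets of tests in SAP 8.3.1 are also not split by arm. The tissue visit contrasts of dose-normalized concentration are by specimen type only, and the within-sex comparisons of penetration between specimen types combine the arms.

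SAP 8.3 defines penetration as the protein-normalized level in the mucosal specimen divided by that in serum, times 100. It calls a result significant if the BH-adjusted p-value or the q-value is at most 0.05, and it runs a paired test with as few as 3 pairs.

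On numbers, Protocol 6.1 plans 24 participants "with 12 participants assigned to each group" and says "the trial will enroll at least and approximately 50% of participants assigned female sex at birth". SAP section 5 adds: "The randomization will be stratified by assigned sex at birth and done in blocks to ensure balance across both groups". Under Protocol 9.6 only participants assigned female at birth give cervical and vaginal biopsies. On missing data, Protocol 6.1 says "17% is a reasonable estimate for the rate of missing data", from vaccine trials, and gives about 10-15% for drug concentrations in the earlier VRC01 trial.

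**The concern.** Splitting by arm halves a sample that is already halved by sex. For cervical and vaginal tissue the discreteness of the signed-rank test then matters more than the data: at these sizes the smallest attainable p-value is near or above 0.05.

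At stake is whether penetration into genital tissue changes between the first and the third infusion. Mucosal levels are a primary endpoint, and Protocol 4.2.1 names accumulation after repeated dosing as something to learn. As planned, a non-significant tissue result based on 5 or 6 pairs would stand beside secretion results based on both arms, and the two would look comparable when they are not.

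**Working it through.** **Inputs.** 12 per arm and about 50% women, balanced by stratification, give about 6 women per arm. The 40-60% imbalance allowed for in Protocol 6.1.2 gives about 5 to 7. Missing data are 10-17% (Protocol 6.1). Tests are two-sided at 0.05 (SAP section 7), followed by BH or the q-value (SAP 8.3).

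**The plan's nearest figure.** The documents give no power for the visit comparison. Protocol Table 6-3 gives 77.2% for a correlation test with n = 6 and r = 0.9, the protocol's own size for one sex within one arm. Using its formula:
- Critical r (t, 4 df, 2.776) = 2.776/√(2.776² + 4) = 0.811, with arctanh 1.131.
- Z′ = arctanh(0.9) + 0.9/10 = 1.562.
- Power = Φ((1.562 − 1.131) × √3) = Φ(0.746) = 77.2%, as stated.

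That figure does not carry over to the signed-rank test.

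**Smallest attainable p-value.** For the exact signed-rank test with n pairs it is 2/2ⁿ.

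| Pairs | Smallest two-sided p |
|---|---|
| 3 | 0.25 |
| 4 | 0.125 |
| 5 | 0.0625 |
| 6 | 0.03125 |
| 7 | 0.0156 |
| 10 | 0.00195 |
| 12 | 0.00049 |

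At 6 pairs the next smallest value is 0.0625, so only six changes in the same direction give p below 0.05.

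**Expected pairs per arm, starting from 6 women.**
- If a person misses both visits or neither: 6 × 0.90 = 5.4 to 6 × 0.83 = 5.0. The chance of all six pairs at 17% is 0.83⁶ = 33%.
- If the two visits go missing independently: 6 × 0.90² = 4.9 to 6 × 0.83² = 4.1. The chance of all six at 17% is 0.83¹² = 11%.

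**FDR.** The SAP does not name the family. If it is one table by arm (3 tissues × 2 arms = 6 tests), p = 0.03125 passes BH only if 0.03125 × 6/k ≤ 0.05. That requires k ≥ 3.75, so at least 4 of the 6 tests must be that small. At 5 pairs the best possible BH value is 0.0625. At 7 pairs, 0.0156 × 6/k ≤ 0.05 requires 2 tests.

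**Power by simulation** (40,000 runs, normal paired differences, exact test, mean change of 1 SD assumed in every tissue). The BH family is 6 tests by arm or 3 pooled.

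| Setting | Power per cervical or vaginal test, BH |
|---|---|
| By arm, 5 pairs | 0% |
| By arm, 6 pairs (rectal 12) | 20% |
| By arm, 7 pairs (rectal 12) | 42% |
| Pooled, 10 women (rectal 20) | 76% |
| Pooled, 12 women (rectal 24) | 84% |

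Before adjustment, the power is 0% at 5 pairs, about 35% at 6 (Φ(1)⁶ + Φ(−1)⁶ = 0.355), 79% at 10 and 85% at 12. If only one genital tissue changes and no data are missing, power after BH is about 0.1% per test by arm against 71% pooled.

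The 10-woman row is 12 × 0.83 = 10.0, with missingness by person. Independent loss at 17% would leave 12 × 0.83² = 8.3 pooled pairs, so power would be below the range shown. The floor would still be low enough: 0.0078 at 8 pairs, times 3, is 0.023.

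**Rectal tissue.** Both sexes contribute, about 12 per arm, with a floor of 0.00049. For a 1 SD change the unadjusted power is about 85% with 12 pairs and 99% with 24.

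**The case against.** A reader might infer that genital tissue cannot give a positive result at all, or that the choice is simply 76% power against 0%. The documents do not support that. The 0% holds at 5 or fewer pairs with an exact test, whereas the planned number is about 6 and the protocol's range reaches 7. For a change of 1.5 SD, power by arm at 6 pairs is about 63% after BH. The SAP does not name the exact version: the normal approximation at 5 pairs gives a smallest p of 0.059 with continuity correction and 0.043 without. It also accepts a q-value, which could occasionally pass where BH does not. The 17% missing rate comes from vaccine trials, and 10-15% from the antibody trial is the closer analogue.

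It is also tempting to say that dose cancels because penetration is a ratio. That assumes equal penetration at both doses. The SAP does not take this for granted: it tests tissue penetration between arms at visit 4 and controls for arm when comparing the sexes. By-arm reporting therefore has some logic. But secretions get the same between-arm test and are still pooled. The signed-rank test also works on within-person changes, so a difference in penetration level between arms does not invalidate pooling. A difference between arms in the change itself would be averaged over.

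Change in penetration is not itself a listed protocol endpoint. The visit 4 versus 8 tissue tests on dose-normalized, IgG-normalized concentrations are not split by arm, and regressions of between-visit differences adjust for treatment group. These soften the gap but do not answer the penetration question. Nothing in the documents says that a null will be reported as no change. The split may be a wording slip between the methods text and the table list.

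**Conclusion.** The point holds for cervical and vaginal tissue. The split by arm is unexplained, differs from the secretion tables and is absent from the methods text. It leaves about 6 women per test, or 5 to 7, before missing data. At 5 or fewer pairs an exact test cannot reject; at 6 it rejects only on a unanimous direction, before adjustment. For a 1 SD change in every tissue the loss after BH is from 76-84% pooled to 0%, 20% or 42% per arm at 5, 6 or 7 pairs. These figures rest on the exact test, normal paired differences, the assumed effect size and one table as the FDR family. Rectal tissue is not subject to the floor, although it loses power too. The change is worth making and small.

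**What to change.** For the visit 4 versus 8 tissue penetration table in SAP 8.3.1, replace the split by arm with the secretion wording, "by specimen types with treatment groups combined", and show the by-arm results descriptively. State that the exact signed-rank test is used, name the FDR family, and make the methods text in SAP 8.3 agree.

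The cost is one phrase and the loss of a formal visit test within each arm. Penetration between the doses is still tested at visit 4.

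The visit 2 versus 9 tissue table carries the same phrase, but visit 2 is before the first infusion and SAP 8.3 excludes pre-treatment data from the analysis. Those two statements must be reconciled before its pooling is decided.
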